6.7. Multicenter Studies

This is a multicenter study. Because there are twelve strata prior to considering site, further stratification by site would result in an excessive number of strata and so randomization is not stratified by site. Therefore, treatment imbalances might by chance occur within sites. Additionally, the potential for site effects on DOOR components is present. Therefore, sensitivity analyses for potential site effects are necessary.

In the primary analysis, data will be pooled across all clinical sites and analyses will not adjust for potential site effects. However, as a sensitivity analysis, the ITT analysis of DOOR at Outcome Assessment Visit #1 will be repeated as a stratified analysis in which each site will be analyzed separately (see Section [8.3.2](#)).

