14.6	Future Use of Stored Specimens	57
15	Data Handling and Record Keeping	58
15.1	Data Management Responsibilities.....	58
15.2	Data Capture Methods.....	58
15.3	Types of Data	58
15.4	Timing/Reports	59
15.5	Study Records Retention	59
15.6	Protocol Deviations.....	59
16	Publication Policy	60
17	Literature References.....	61
	APPENDIX A – Schedule of Evaluations.....	62

LIST OF FIGURES AND TABLES

Figure 1: Study Schematic	X
Table 1. Ordinal Outcome	16
Table 2: Severity of Cough.....	17
Table 3. Solicited Events Grading	17

LIST OF ABBREVIATIONS

AE	Adverse Event/Adverse Experience
ARLG	Antibiotic Resistance Leadership Group
ATP	According-to-Protocol
CAP	Community Acquired Pneumonia
CC	Complete Case
CFR	Code of Federal Regulations
CMS	Clinical Materials Services
DHHS	Department of Health and Human Services
DMID	Division of Microbiology and Infectious Diseases, NIAID, NIH, DHHS
DOOR	Desirability of Outcome Ranking
DSMB	Data and Safety Monitoring Board
eCRF	Electronic Case Report Form
ED	Emergency Department
EHR	Electronic Health Record
FDA	Food and Drug Administration
FWA	Federalwide Assurance
GCP	Good Clinical Practice
HIPAA	Health Insurance Portability and Accountability Act
ICH	International Conference on Harmonisation
ICMJE	International Committee of Medical Journal Editors
IDES	Internet Data Entry System
IDSA	Infectious Diseases Society of America
IEC	Independent or Institutional Ethics Committee
IND	Investigational New Drug Application
IRB	Institutional Review Board
ISM	Independent Safety Monitor
ITT	Intention-to-Treat
MOP	Manual of Procedures
NIAID	National Institute of Allergy and Infectious Diseases, NIH, DHHS
NIH	National Institutes of Health
OHRP	Office for Human Research Protections
PI	Principal Investigator
QA	Quality Assurance
QC	Quality Control
RADAR	Response Adjusted for Days of Antibiotic Risk
SAE	Serious Adverse Event/Serious Adverse Experience
SDCC	Statistical and Data Coordinating Center
SUSAR	Suspected Unexpected Serious Adverse Reaction
US	United States
USP	United States Pharmacopeia

PROTOCOL SUMMARY

Title:	A Phase IV Double-Blind, Placebo-Controlled, Randomized Trial to Evaluate Short Course vs. Standard Course Outpatient Therapy of Community Acquired Pneumonia in Children (SCOUT-CAP)
Phase:	IV
Population:	Approximately 400 subjects aged 6-71 months of age with community acquired pneumonia (CAP)
Description of Sites/Facilities Enrolling Participants:	5 to 10 US outpatient sites
Study Duration:	25 months

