4.4.2. Method of Assigning Subjects to Treatment Groups (Randomization)

Per International Conference on Harmonisation (ICH) guideline E6: Good Clinical Practice (GCP), screening records will be kept at each participating site to document the reason why an individual was screened, but failed trial entry criteria. The reasons why individuals failed screening will be recorded on screening logs maintained by each site.

Once consented and upon entry of demographic data and confirmation of eligibility for this trial, the subject will be enrolled. Subjects will be assigned to either placebo or active study drug (the same antibiotic that they were prescribed for the first 5 days of treatment). After a subject is enrolled, they will be given a random treatment assignment of study product to either short course or standard course therapy. Randomization to short vs. standard course therapy will be at a 1:1 ratio (approximately 200 subjects per treatment group). Subjects will be stratified by age group <24 months vs. 24-71 months), type of initial antimicrobial therapy, and initial treatment in an ED or outpatient clinic/urgent care center.

Enrollment of subjects will be performed online using the electronic data capture (EDC) system provided by the Statistical and Data Coordinating Center (SDCC). The list of randomized treatment assignments will be prepared by statisticians at the SDCC. The list will be used to assign each volunteer a treatment code after the necessary data have been entered into the EDC

system. A designated individual at each site will be provided with a treatment key, which links the treatment code to the actual treatment assignment, which will be kept in a secure place.

Instructions for subject enrollment are included in the Manual of Procedures (MOP). Manual back-up randomization procedures are provided in the MOP for use in the event that the site temporarily loses access to the Internet or the online enrollment system is unavailable.

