5. SAMPLE SIZE CONSIDERATIONS

The null hypothesis corresponding to the primary analysis of this study is:

H0: The sum of the probability that a subject assigned to the 5-day arm will have a higher DOOR than if assigned to the 10-day arm plus one-half the probability of equal DOORs is 50% (i.e., no difference in DOOR).

The primary study sample size is based on a superiority test of the null hypothesis above, under an assumed alternative hypothesis that the sum of the probability that a subject assigned to the 5-day arm will have a higher DOOR than if assigned to the 10-day arm plus one-half the probability of equal DOORs is 60% (p=60%).

A sample size of 360 (180 per arm) provides 90% power using a 2-sided alpha=0.05 with a Wilcoxon Mann-Whitney U test (see calculation below). If p=65% or 70%, then a total sample size of 160 (80 per arm) or 90 (45 per arm), respectively, would be required. The sample size is inflated by ~10% based on an estimate from a similar study, in order to account for loss to follow-up resulting in a total sample size of 400 (200/arm).

Sample size calculations were based on the formula below (Noether 1987):

$$N = \frac{(z_{\alpha} + z_{\beta})^2}{12c(1-c)\left(p'' - \frac{1}{2}\right)^2}$$

$$z_{\alpha} = \Phi^{-1}(0.975); z_{\beta} = \Phi^{-1}(0.90); (90\% \text{ power for two-sided test with } 5\% \text{ Type I error})$$

$$c = 0.5 \text{ (equal allocation to treatment arms)}$$

$$p'' = 0.6 \text{ (Pr(Higher DOOR) under alternative hypothesis)}$$

Note that the primary analysis statistical methods use the ITT analysis population and will account for missing data with multiple imputation. The exact analysis method was not used for the power calculation because it would require an excessive amount of assumptions about the nature and patterns of missing data in the final dataset and relationships of components of the imputation model to the primary outcome. Instead, a complete case analysis assuming 90% evaluable for analysis was used to obtain approximately 90% power in the actual analysis.

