8.3.2. Stratified (ITT) Analyses of DOOR at Outcome Assessment Visit #1

Analysis of DOOR at Outcome Assessment Visit #1 as described in Section 8.1.1 will be performed separately for each level of each stratification variable (e.g. an analysis of all subjects of age <24 months at enrollment, and a separate analysis of all subjects of age 24-71 months at enrollment) and by clinical site. Results will be reported [Table 47](#).

8.3.3. As Treated Analysis of Effect of Number of Days of Antibiotic Use on OCR at Outcome Assessment Visit #1 and Outcome Assessment Visit #2

The analysis will be performed using the subset of the CC-V1 analysis population that did not receive off-study systemic antibiotic unrelated to pneumonia prior to Outcome Assessment Visit #1. The justification for excluding subjects with unrelated antibiotic use is that subjects receiving unrelated antibiotics are at risk for both improved outcomes due to ongoing antibiotic use as well as increased side effects related to antibiotics administration. The effect of the number of days of antibiotic use at Outcome Assessment Visit #1 on OCR at Outcome Assessment Visit #1 will be analyzed using a proportional odds model that simultaneously uses all cumulative logits (Agresti 2003).

Let \mathbf{K} be the set of distinct OCR values observed at Outcome Assessment Visit #1, with the exception that the highest (worst) distinct value observed is not included in the set.

Let Y_i = the OCR of subject i at Outcome Assessment Visit #1.

Let X_i = the number of days of antibiotic use at Outcome Assessment Visit #1 for subject i .

α_k , where $k \in \mathbf{K}$, and β are parameters to be simultaneously estimated through maximum likelihood methods.

Then, proportional odds model with cumulative logits is defined as

$$\text{Logit } [P(Y_i > k)] = \alpha_k + \beta X_i, \quad k \in \mathbf{K}$$

The following gives the interpretation of the model. Suppose D is any non-negative integer.

$$\text{Then, } \log[\text{odds}(\text{OCR} > k \mid X_i = D+1) / \text{odds}(\text{OCR} > k \mid X_i = D)] = \beta.$$

That is, for any k , where k is from the set of observed OCR values at Outcome Assessment Visit #1 besides the highest observed value, e^β gives the odds ratio of an OCR at Outcome Assessment Visit #1 greater than k for the effect of one additional day of use of antibiotic.

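### The site sensitivity analysis gives only separate per-site results, so no site-adjusted overall DOOR estimate is planned to set beside the pooled primary result

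*SAP*

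**What the plan says.** SAP Section 6.7 explains that there are already twelve randomization strata, so site was left out. It accepts that the arms may by chance be unbalanced within sites and that sites may differ on the DOOR components, and concludes: "Therefore, sensitivity analyses for potential site effects are necessary". The primary analysis pools the sites without adjustment. As the check, the ITT analysis of DOOR at Outcome Assessment Visit #1 "will be repeated as a stratified analysis in which each site will be analyzed separately".

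SAP Section 8.3.2, which sits under the exploratory analyses, gives the method: the Section 8.1.1 analysis "will be performed separately for each level of each stratification variable", and the same sentence extends this to clinical site. The Table 47 shell has one estimate, confidence interval and p-value per level or site, and no combined row. SAP Section 10 plans nothing further, and Protocol Section 11.4 names no site-adjusted analysis.

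Site appears elsewhere in three ways: as predictors in the imputation model (SAP 8.4.1), as first-treatment counts by site and arm (Table 6), and as baseline rows by arm (Table 11). The Protocol Summary gives "5 to 10 US outpatient sites". The SAP shells name five sites, with others added if they enroll. Neither document gives expected site sizes.

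**The concern.** The worry stated in Section 6.7 has two parts that matter jointly: arms unbalanced within sites, and sites that differ in outcome. Together they can move the pooled estimate. The natural check is an overall estimate in which children are compared only with children at the same site, read beside the primary one. The plan makes the within-site comparisons but never brings them together. The reader gets five to ten imprecise site results and must judge from those whether the pooled result would stand after allowing for site.

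**Working it through.** **Inputs.** Two-sided alpha 0.05, 90% power, 360 evaluable, target probability 0.60 against 0.50, 400 randomized 1:1 (SAP Section 5); 5 to 10 sites (Protocol Summary). Assumptions: equal site sizes unless stated, arms balanced within site, no ties, and a true probability of 0.60 at every site for the power figures. Ties would narrow all the intervals below.

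**1. The plan's own figure.** Noether: N = (1.960 + 1.282)² / [12 × 0.25 × (0.60 − 0.50)²] = 10.507 / 0.03 = 350.2, so 351. The SAP says: "A sample size of 360 (180 per arm) provides 90% power using a 2-sided alpha=0.05 with a Wilcoxon Mann-Whitney U test". That is slightly above the formula; power at 360 is Φ(√(3 × 360) × 0.1 − 1.96) = 90.8%. Inflation gives 360 / 0.90 = 400. The sample size is sound.

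**2. Precision of one site alone.** For n subjects split equally, the null standard error of U/(n1·n2) is √[(n + 1) / (12 × (n/2)²)], and power is Φ(√(3n) × 0.1 − 1.96).

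| Analysis | n | 95% half-width | Power at 0.60 |
|---|---|---|---|
| Pooled | 400 | 1.96 × √(401/480,000) = 0.057 | 93.4% |
| One of 5 equal sites | 80 | 1.96 × √(81/19,200) = 0.127 | 34% |
| One of 10 equal sites | 40 | 1.96 × √(41/4,800) = 0.181 | 19% |

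With assumed unequal shares of 40, 25, 15, 12 and 8% (160, 100, 60, 48 and 32 subjects), half-widths run from 0.090 to 0.203 and power from 59% down to 16%.

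If there is no effect and the sites are independent, the chance of at least one site p-value below 0.05 is 1 − 0.95⁵ = 23% with five sites and 1 − 0.95¹⁰ = 40% with ten.

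**3. The same site results combined.** With equal sites, the inverse-variance combination has variance equal to the single-site variance divided by the number of sites.

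- Five sites: √(0.004219/5) = 0.02905, half-width 0.057, power Φ(0.1/0.02905 − 1.96) = 93.1%.
- Ten sites: √(0.008542/10) = 0.02923, half-width 0.057, power 92.8%.
- The unequal shares above: half-width 0.057, power 93.1%.
- At 360 subjects: 90.4% (five sites) and 90.0% (ten), against 90.8% pooled.

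The largest loss is 90.8 − 90.0 = 0.8 points. The pooled power uses Noether's approximation and the stratified power the (n + 1) variance, so the loss is if anything slightly overstated.

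**4. How far pooled and site-stratified estimates might differ.** The documents give no site-effect sizes, so this is illustration only. It is a simulation with 400 subjects, the unequal shares above, 200 per arm allocated without regard to site, a continuous outcome, no treatment effect and 2,000 replicates. The 95th percentile of the absolute gap was 0.008 with no site effect, 0.025 with a between-site SD of half the residual SD, and 0.040 with the two SDs equal. The design difference is 0.60 − 0.50 = 0.10.

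**The case against.** Section 6.7 asks for sensitivity analyses for site effects; it does not promise an adjusted overall estimate. Per-site estimates show whether the effect is similar across sites or driven by one, and each is free of between-site confounding. A reader might infer that the planned analysis says nothing useful about site. That goes too far: it is a legitimate description of heterogeneity.

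A reader might also infer that within-site imbalance goes unexamined. It does not, because Tables 6 and 11 display arm counts by site. What they cannot show is what any imbalance does to the estimate.

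The term stratified is defined in the sentence that uses it, and Sections 6.7 and 8.3.2 and Table 47 agree, so no programmer would be misled. The absence of multiplicity correction is openly declared in Section 6.8. The primary analysis also leaves out the actual randomization factors, so adjusting for site is one reasonable choice among several. Finally, a reader could form a rough weighted average from the Table 47 rows.

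Most of this stands and limits the point. Two things remain. The SAP itself singles out site and calls the check necessary. And a hand-made average would rest on rounded figures and on weights chosen after the results are known, which pre-specification is meant to avoid.

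**Conclusion.** The gap is real but confined to a sensitivity analysis: no combined site-adjusted estimate, interval or p-value is planned. Per-site half-widths of about 0.13 (five equal sites) to 0.18 (ten, the protocol's upper bound) exceed the design difference of 0.10, so the site rows are a weak check on a pooled result whose half-width is 0.057. Equal site sizes and no ties are assumptions.

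Two stronger inferences are not supported. One is that the primary test is invalid or its type I error inflated; individual randomization keeps the unadjusted test valid whether or not site was a stratum. The other is that the half-widths show how far the pooled result would move after site adjustment. They measure site-level imprecision only. The simulated gaps of 0.008 to 0.040 speak to movement, but they rest on site effects that no document supplies.

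This is a cheap improvement worth making, and nothing in the primary inference depends on it.

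**What to change.** In SAP Sections 6.7 and 8.3.2, add a site-stratified Mann-Whitney (van Elteren-type) sensitivity analysis of DOOR at Outcome Assessment Visit #1 in the ITT cohort:

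- Reuse the 20 imputed datasets of the primary analysis; the imputation model already contains site.
- In each dataset, compute U/(n1·n2) within each site, with null variance {(n + 1) − Σ(t³ − t)/[n(n − 1)]} / (12·n1·n2), where n is the site total and t the size of each tied group within the site.
- Combine sites with pre-specified inverse-variance weights. Without ties these are 12·n1·n2/(n + 1), the van Elteren weights.
- Pool over the 20 imputations by Rubin's rules, as in Section 8.1.1.
- Pre-specify, before unblinding, how small sites or sites lacking one arm are merged.
- Report the combined estimate, 95% confidence interval and p-value as an extra row in Table 47. Present the per-site rows as descriptive estimates with intervals, without p-values.

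Add one sentence on interpretation: the combined figure compares only children at the same site, so if sites differ strongly and treatment has an effect, it need not equal the pooled probability even under perfect balance.

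The cost is a little more programming and under one point of power relative to the pooled test, in a sensitivity analysis only. The primary analysis and sample size do not change.

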6.8. Multiple Comparisons/Multiplicity

Only one hypothesis test will be performed for the primary analysis. Secondary and exploratory analyses will not be corrected for multiplicity.

7. STUDY SUBJECTS

7.1. Disposition of Subjects

Reasons for screening failures will be summarized in [Table 8](#). The completion status and reasons for early termination or treatment discontinuation will be summarized ([Table 4](#) and [Listing 1](#)). A subject could be discontinued early due to an AE (serious or non-serious), loss to follow-up, non-compliance with study, voluntary withdrawal by parent/guardian, withdrawal at the investigator request, termination of the site by the sponsor, termination of the study by the sponsor, death, lack of eligibility at enrollment, or becoming ineligible after enrollment.

Subject disposition and eligibility for analysis will be summarized in a CONSORT flow diagram ([Figure 2](#)).

7.2. Protocol Deviations

A summary of subject-specific protocol deviations will be presented by the reason for the deviation, the deviation category, and treatment group for all subjects ([Table 2](#) and [Listing 2](#)). Non-subject specific protocol deviations will be in [Listing 3](#). All subject-specific protocol deviations and non subject-specific protocol deviations will be presented. Major protocol deviations (see Section [6.3.3](#)) will be discussed.

8. EFFICACY EVALUATION

All efficacy variables will be listed by subject. Data will be summarized by treatment group. Continuous efficacy variables will be summarized with the number of observations, mean, median standard deviation, minimum and maximum. Categorical efficacy variables will be summarized by number and percent in each category.

All statistical tests are two-sided and performed at the $\alpha=0.05$ significance level.

8.1. Primary Efficacy Analysis

The primary efficacy analyses will be performed for the ITT cohort.

8.1.1. Primary Analysis of DOOR at Outcome Assessment Visit #1

DOOR at Outcome Assessment Visit #1 is defined in Section 3.3.

The null hypothesis corresponding to the primary analysis of this study is:

H0: The sum of the probability that a subject assigned to the 5-day arm will have a higher DOOR at Outcome Assessment Visit #1 than if assigned to the 10-day arm plus one-half the probability of equal DOORs at Outcome Assessment Visit #1 is 50% (i.e., no difference in DOOR at Outcome Assessment Visit #1).

The above null hypothesis can be tested using a Mann-Whitney U Test (Evans 2015).

The primary analysis will use multiple imputation with a linear model to impute missing DOOR at Outcome Assessment Visit #1 outcomes. Details of multiple imputation methods are described in Section 8.4.1.

For each of the 20 complete multiply imputed datasets, a Mann-Whitney U statistic will be computed using randomization to short course versus randomization to standard course to define the binary grouping and DOOR at Outcome Assessment Visit #1 as the outcome. The U statistics are asymptotically normal distributed, and so they can be combined into a single test statistic using Rubin's Rules (Marshall 2009).

Defining the following:

n_1 : number of subjects in ITT cohort randomized to a short course of antibiotics

n_2 : number of subjects in ITT cohort randomized to a standard course of antibiotics

m : number of imputed datasets ($m = 20$)

Q_i : U statistic computed from the i^{th} multiply imputed dataset

$$\bar{Q} = \frac{1}{m} \sum_{i=1}^m Q_i$$

Q_0 : the expected value of a U statistic under the null hypothesis ($Q_0 = \frac{n_1 n_2}{2}$)

\bar{U} : The within imputation variance (this is not the mean of the U statistics). Correcting for ties, the formula for the within imputation variance of U is:

$$\bar{U} = \text{Var}(Q_i) = \frac{n_1 n_2}{12} \left[(n_1 + n_2 + 1) - \sum_{c=1}^D (M_c^3 - M_c) \right] \quad (\text{Lehmann 1975, Zhao 2008}),$$

where M_c is the number of tied ranks for the c^{th} value DOOR in the dataset and D is the number of distinct values of DOOR in the dataset. Because the numbers of tied ranks should be very similar across the 20 multiply imputed datasets, the number of ties will be counted from the first imputed dataset only, and those counts will be used to compute the corrected variance.

$$B = \frac{1}{m-1} \sum_{i=1}^m (Q_i - \bar{Q})^2$$

$$T = \bar{U} + \frac{m+1}{m} B$$

$$W = \frac{(\bar{Q} - Q_0)^2}{T}$$

$$r = \frac{m+1}{m} \frac{B}{\bar{U}}$$

$$\nu = (m - 1) \left(1 + \frac{1}{r}\right)^2$$

Under null hypothesis corresponding to the primary analysis of this study,

$$W \sim F_{1,\nu}$$

This F-distribution is used to compute a p-value (one-sided probability) from the overall test statistic W . The null hypothesis will be rejected if $p < 0.05$.

A corresponding 95% confidence interval for U will be computed using the overall test statistic W through the inversion of the F-test. Dividing the bounds of this confidence interval by $n_1 n_2$ will yield the bounds for the 95% confidence interval of $\Pr(\text{Higher DOOR in short course}) + 0.5 \Pr(\text{Equal DOOR in short course})$. Thus, the confidence interval is given by:

$$95\% \text{ CI: } \left(\frac{\bar{Q} - \sqrt{T \times F_{0.95,1,\nu}}}{n_1 n_2}, \frac{\bar{Q} + \sqrt{T \times F_{0.95,1,\nu}}}{n_1 n_2} \right)$$

A point estimate of the probability will be obtained by dividing \bar{Q} by $n_1 n_2$. Results will be shown in [Table 14](#).

